6.1 Screening/Baseline Visit

The appropriate baseline assessments for the LTE ([Table 1 Schedule of Assessments](#)) will be collected at the end of study visit (Week 24) for AV-101-002. Depending on outcome for analysis, baseline values reported during the parent trial may be used especially among subjects randomized to active treatment groups. Following Day 1 in the LTE, all subjects will have a telephone visit at Week 1 (7 days) for safety follow up.

Safety

- Review prior (within the past 30 days) and current concomitant medications and therapies
- Record AEs

Randomization

Subjects who were on placebo and entering the LTE from the Phase 2b and Intermediate Parts of Study AV-101-002 will be centrally randomized via an IWRS.

6.2 Post-Screening/Baseline Visits

Assessments to be performed for each visit are outlined in the Schedule of Assessments ([Table 1](#)). At each of the clinic visits where study drug dispensing is required, site staff will contact the IWRS to obtain the appropriate kit numbers and the specified kit(s) will be dispensed.

6.2.1 Telephone Visits

Telephone Contacts are required at Week 1, Week 8, Week 16 and Safety FU. AE, Concomitant Medications, Clinical Worsening and Vital Status (when required) must be assessed. For women of childbearing potential, a reminder to perform home pregnancy testing is also provided during the telephone visits including an additional call at Week 20. In addition, Investigators are required to evaluate subjects for the presence of any signs or symptoms suggestive of intracranial bleeding such as: headache, confusion, vomiting, slurred speech, etc.

6.2.2 Early Discontinuation Visit

Criteria for discontinuation are provided in [Section 6.8](#). Subjects discontinuing study treatment must return to the site within 14 days for safety assessments. If this assessment does not correspond with a scheduled study visit, then an Early Discontinuation (ED) Visit will be performed.

Should a subject withdraw consent to be followed, they should return for an ED Visit within 14 days following the last dose and will have a Safety FU 4 weeks after the ED Visit. As many of these assessments as possible should be conducted.

If the subject is unwilling or unable to come into the clinic for the ED Visit, then this visit with as many assessments as possible can be conducted by telephone.

6.2.3 End of Treatment Visit

In a small cohort of subjects treated with oral imatinib for PAH, a responder analysis showed that the treatment duration for a complete hemodynamic response was approximately 3 years (Speich, 2015). Therefore, the LTE study will continue until 31 December 2025 or until the Sponsor stops the study.

Subjects may be able to receive expanded access supply of AV-101 should it be approved by regulatory authorities and available commercially in other countries or regions of the world. If AV-101 is not approved by either the FDA or EMA, then expanded access supply will be considered on a case-by-case basis.

6.2.4 Safety Follow Up Period

After the last dose of the IMP, subjects will be required to enter a 30-day Safety Follow Up Period.

Subjects who complete an ED Visit are also required to complete the 30-day Safety Follow Up Period.

Subjects will be contacted 30 days (± 2 days) after the ED Visit to review adverse events and concomitant medications. Ongoing AEs will be followed as outlined in Section 7.4. Subjects will then be contacted for Vital Status every 24 weeks after the Safety Follow Up Visit by telephone until study completion.

6.3 Demographic and Other Baseline Characteristics

Demographic data such as year of birth, self-reported race (Note: in France race is not recorded) and ethnic origin, gender, weight, (BMI will be automatically calculated in the eCRF), will be assessed at baseline. Information about previous and concomitant medications will also be recorded.

PAH is a rare disease, and this study is the first evaluation of the long-term safety of AV-101 in patients with PAH. Race and ethnicity are collected, where permitted, to support the understanding if potential ethnic differences exist in exposure and/or response to the investigational product among different ethnic groups.

Complete medical and disease history will be recorded. All ongoing conditions and relevant/significant medical history (including cardiovascular history, all major hospitalizations and surgeries) will be recorded at the baseline visit in the parent study. Should there be significant changes in medical and disease history upon entry into the LTE, these changes will be recorded. Symptoms related to PAH and/or the underlying etiology of the disease need not be listed on the medical history form; however, worsening of any symptoms during the course of this study must be captured as an AE.

Other baseline measurements such as physical examination, safety laboratory parameters, ECG, and vital signs will be recorded in the eCRF.

6.4 Effectiveness Assessments and Procedures

Assessments for the effectiveness endpoints will be evaluated based on the visits specified in the Schedule of Assessments ([Table 1](#)).

6.5 Safety Assessments and Other Study Procedures

Safety will be assessed by physical examinations, vital signs, ECGs, clinical laboratory tests, pulmonary function (spirometry) tests and evaluation of AE/SAEs.

Comprehensive assessment of any apparent toxicity experienced by the subject will be performed throughout the course of the study, starting from the time of the subject's signature of informed consent. Study site personnel will report any AE, whether observed by the Investigator or reported by the subject ([Section 7.1](#)).

Adverse events of special interests (AESI) are peripheral edema, periorbital edema, facial edema, nausea, vomiting, diarrhea, anemia, subdural hematoma, pneumonia, upper and lower respiratory tract infection, oral candidiasis, severe cough, and wheezing. These are clinically important events seen with oral imatinib, and/or other events important with respect to inhaled medications.

Given the occurrence of subdural hematomas in the IMPRES study, Investigators should be alert and routinely question subjects as to any symptoms suggestive of intracranial bleeds including headache, confusion, vomiting, slurred speech, etc. If such signs and/or symptoms are present, then appropriate further investigations should be undertaken.

6.5.1 Physical Examinations

Investigators should pay special attention to clinical signs related to previous serious illnesses.

At Screening/Baseline and all post-baseline clinic visits, a focused physical examination will be performed, and will include assessments of the skin, HEENT, thorax/lungs, abdomen, and cardiovascular, musculoskeletal and neurological systems, as well as any new subject complaints or changes from baseline.

Any clinically significant findings collected prior to the LTE study consent will be documented as medical history. Any new or worsening abnormal physical examination findings collected after the LTE consent that are considered clinically significant by the Investigator should be reported as AEs and recorded in the AE eCRF if the finding meets the definition of an AE.

6.5.2 Vital Signs

Vital sign measurements (BP, pulse rate, temperature, respiratory rate), weight and height will be collected prior to any other study-related procedures, at the visits specified in [Table 1](#).

- Temperature, pulse rate, respiratory rate

- Blood pressure and pulse measurements will be assessed with the subject seated with a completely automated device. Manual sphygmomanometer can be used only if an automated device is not available.
 - Blood pressure and pulse measurements should be preceded by at least 5 minutes of rest for the subject in a quiet setting without distractions (e.g., television, cell phones)
- Vital signs are to be taken before blood collection for laboratory tests.
- Height will be recorded at the Screening/Baseline Visit using the measurement value taken from AV-101-002. Body weight will be measured with a balance beam scale, if possible.

6.5.3 Resting Electrocardiogram (ECG)

Digital 12-lead ECGs for all subjects will be recorded at the site using an appropriate ECG machine.

- A standard, single, digital 12-lead ECG will be obtained as outlined in the Schedule of Assessments after the subject has been resting in the supine position for 5 minutes using an ECG machine that automatically calculates the heart rate and measures PR, RR, QRS, QT, and QTc intervals.

All digital ECGs will be documented by recording date and time of collection. All ECG results must be reviewed at the site by the Investigator or a medically qualified designee for clinical management of the subject. The Investigator will judge the overall interpretation as normal or abnormal. Clinical significance and the reason for the abnormality will be recorded in the source documents and in the eCRF. Abnormal values will not be recorded as AEs unless they are a clinically significant change and/or the reason for discontinuation of the study drug due to AEs or are SAEs.

If an ECG result reveals a QTc interval that exceeds 500 msec, or a QTc progression of ≥ 60 msec from baseline, the subject must follow the instructions for down titration of investigational product per [Section 5.5](#) (Also see [Section 5.9.2](#)).

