5.5 Down Titration

If a subject down titrated the dose of AV-101 in Study AV-101-002 and successfully completed 24 weeks of treatment, the subject should begin the LTE study with 2 capsules BID at the assigned dose i.e., either re-randomized if coming from placebo or continuing on the randomized dose but at two capsules BID if on active. If the subject does not tolerate the 2 capsules, they may down titrate to one capsule in the LTE. At the time of optimal dose selection and the transition to the optimal dose in subjects who have down titrated in the LTE, the investigator should decide whether it is clinically appropriate to transition these subjects to the optimal dose given the tolerability history and optimal dose selection (Investigators will be unblinded to treatment dose at this time). E.g., if a subject in the 10 mg dose group has to down titrate to one capsule (5 mg) then it is likely inappropriate to transition the subject to 70 mg if that is the chosen optimal dose for Phase 3 and LTE; however, this decision should be based on the Investigator's opinion. Down titration to one capsule BID after being switched to the optimal dose in the LTE will be permitted.

If a subject develops intolerable adverse events during the study, a down titration from two capsules to one capsule will be allowed. The Investigator should conduct an Unscheduled telephone or video visit with the subject to discuss and decide whether down titration to a lower dose is warranted. Careful consideration should be made whether to down titrate or not, and the decision to down titrate should be made when the alternative would be to withdraw study treatment due to drug intolerability. The Investigator should capture any adverse or clinical worsening events, and in cases where the Investigator agrees that down titration is appropriate, the CRO Medical Monitor should be notified as soon as possible. Subjects will not be allowed to up-titrate after having down titrated.

If it is determined by the Investigator that down titration is warranted, the subject will be instructed to take only 1 capsule BID from the assigned study drug bottles. The date and reason for down titration must be recorded in the subject's source documents and in the eCRF.

Down titration is also required if an ECG reveals, for a subject, a QTc interval that exceeds 500 msec, or a QTc progression of ≥ 60 msec (see [Section 5.9.2](#)).

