5.9.2 Prohibited Medicines

The following treatments are not permitted during the study:

- Inhaled prostacyclin therapies
- Warfarin (or any vitamin K antagonists), DOACs or dual antiplatelet therapy

Use of any of the above nonpermitted medicines and therapies require IMP discontinuation (see [Section 6.8](#)) (anti-platelet monotherapy with e.g. aspirin or clopidogrel is allowed).

The use of strong CYP3A4 inhibitors may increase the systemic exposure to imatinib. Likewise, strong CYP3A4 inducers may decrease the exposure of imatinib. It is unknown what contribution of systemically circulating AV-101 will contribute to potential efficacy or adverse events and so alternatives to strong CYP3A4 inhibitors or inducers should be considered.

High doses of oral imatinib are known to have the potential to prolong the QTc interval on the ECG. Drugs that are known to increase the QT interval should be used with caution. For a list of such drugs please refer to <https://crediblemeds.org>. In the event that a subject develops an absolute prolongation of the QTc interval to a value > 500 msec, or develops a change from baseline in the QTc interval of ≥ 60 msec, the subject should undergo a dose reduction. If a subject has already undergone a dose reduction for other reasons, then they should discontinue study drug. The subject should return for an unscheduled visit after two weeks of dose reduction and the ECG should be repeated. If there is a shortening of the QTc interval to < 500 msec, or the change from baseline is

now < 60 msec, the subject should remain on the reduced dose. If there is no change in the QTc interval after reducing the dose then the subject should be discontinued from study drug.

6 Study Assessments and Procedures

Before subjects commence any study-specific activities or procedures, including Week 24 assessments from AV-101-002 which will serve as baseline for this study, the Sponsor requires a copy of the study site's written Independent Ethics Committee/Institutional Review Board (IEC/IRB) approval of the protocol, informed consent form (ICF), and all other subject information and/or recruitment material, if applicable. Each subject must sign and date the ICF before participating in study-specific activities. If an unexpected circumstance occurs that would prohibit the subject from entering the study at Week 24 on AV-101-002, this may be discussed with the CRO Medical Monitor and/or Sponsor.

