- Grade 4** Life-threatening consequences; urgent intervention indicated
- Grade 5** Death related to an AE, Abnormal Laboratory Findings and Other Abnormal Investigational Findings

Abnormal laboratory findings and other abnormal investigational findings (e.g., on an ECG trace) should not be reported as AEs unless they are associated with clinical signs and symptoms, lead to study drug discontinuation or are considered otherwise medically important by the Investigator. Laboratory abnormalities that require medical intervention or lead to study drug interruption, modification, or discontinuation must be recorded as an AE. If a laboratory abnormality fulfills these criteria, the identified medical condition (e.g., anemia or increased alanine aminotransferase) must be reported as the AE rather than the abnormal value itself.

The severity of abnormal laboratory values should be evaluated according to the CTCAE and recorded per the Qualitative Toxicity Scale, as follows:

- Mild:** CTCAE Grade 1
- Moderate:** CTCAE Grade 2
- Severe:** CTCAE Grade 3 and 4

For AEs associated with laboratory abnormalities, the event should be graded on the basis of the clinical severity in the context of the underlying conditions; this may or may not be in agreement with the grading of the laboratory abnormality.

See [Section 7.7](#) for additional details on how to manage AEs associated with abnormal laboratory findings.

3) Causality

The Investigator will establish the causality of the AE or ADE to the experimental treatment. The Investigator will use clinical judgement and should consider the participant's history, most recent physical examination findings, and concomitant medications when assessing causality. For the purpose of clinical study AE reporting, AEs or ADEs should be classified as "Not Related" or "Related" to study treatment or to the device, respectively.

Not Related: There is no reasonable temporal or causal relationship between the study drug, device, or procedure and the event. A reasonable alternative explanation must be available.

Related: There is a reasonable possibility of a temporal and causal relationship between the study drug, device, or procedure and the event.

Events that Do Not Meet the Definition of an SAE

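### A QTc finding that forces the protocol's own dose reduction need not be recorded as an adverse event, whereas a laboratory finding with the same consequence must be

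*Combined protocol and SAP*

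**What the plan says.** **Dose action.** Section 5.5 states: "Down titration is also required if an ECG reveals, for a subject, a QTc interval that exceeds 500 msec", or progresses by at least 60 msec. Section 6.5.3 repeats both thresholds and says that "the subject must follow the instructions for down titration of investigational product per" Section 5.5. Section 5.9.2 says that if a subject "develops a change from baseline in the QTc interval of ≥ 60 msec, the subject should undergo a dose reduction", and treats a value above 500 msec in the same way. It also provides for a repeat ECG after two weeks on the reduced dose. Drug is stopped if the subject had already been reduced for another reason, or if QTc does not change after the reduction.

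**AE recording for ECGs.** Section 6.5.3: "Abnormal values will not be recorded as AEs unless they are a clinically significant change and/or the reason for discontinuation of the study drug". The sentence ends by qualifying the discontinuation ground and adding another: "the reason for discontinuation of the study drug due to AEs or are SAEs". On who reads the trace: "The Investigator will judge the overall interpretation as normal or abnormal". Section 7.1.1, which names ECG traces as an example, says abnormal findings "should not be reported as AEs unless they are associated with clinical signs and symptoms, lead to study drug discontinuation", or are otherwise medically important in the Investigator's opinion.

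**AE recording for laboratory values.** The next sentence of 7.1.1 reads: "Laboratory abnormalities that require medical intervention or lead to study drug interruption, modification, or discontinuation must be recorded as an AE".

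**The concern.** The dose action on a QTc finding is compulsory, but whether the finding becomes an AE can rest on judgement alone. A blood result that leads to the same change in study drug must be recorded. The protocol gives no reason for the difference.

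Long-term safety is the primary objective, and the main safety outputs in Section 8.6 (TEAEs by system organ class and preferred term, treatment-related AEs, severity and relationship) count recorded AEs. The dose consequence can also last: 5.9.2 keeps a subject whose QTc has come down on the reduced dose, and 5.5 bars later up-titration. With approximately 140 sites, a rule left to judgement may be applied differently from site to site.

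**Working it through.** There is no plan figure to reproduce and no arithmetic to run. The check is a comparison of rules, followed by one case traced through them.

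**Grounds for recording an abnormal finding as an AE**

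| Ground | ECG rule, 6.5.3 | General rule, ECG named, 7.1.1 | Laboratory abnormality, 7.1.1 (general rule plus its own sentence) |
|---|---|---|---|
| Clinically significant or medically important (Investigator) | yes | yes | yes |
| Signs or symptoms | not listed | yes | yes |
| Serious event | yes | not listed | not listed |
| Discontinuation of drug | yes, if due to AEs | yes | mandatory |
| Interruption of drug | not listed | not listed | mandatory |
| Modification of drug | not listed | not listed | mandatory |

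**Case traced.** A subject on two capsules BID has no symptoms, and a scheduled ECG shows a QTc rise of at least 60 msec.

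1. Sections 5.5, 5.9.2 and 6.5.3 all lead to a dose reduction. Section 5.5 lists this trigger separately from reduction for intolerable adverse events, so the reduction does not presuppose an AE.
2. There are no symptoms, the event is not serious and drug is not stopped. Three of the four ECG grounds fail.
3. The remaining ground is the Investigator's view of significance or importance. If that view is negative, neither 6.5.3 nor 7.1.1 calls for an AE.
4. Without an AE record, the event does not enter the TEAE or treatment-related tables in 8.6. The CTCAE grade and relatedness (7.1.1) and the outcome (7.5) are asked for as part of AE assessment and reporting, so none is required here.
5. Section 8.6 names a table of AEs leading to withdrawal and none for AEs leading to dose reduction. Adding one would not recover the event, because it was never an AE.

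**Where the gap closes.** If the subject had already been reduced, or QTc does not change after reduction, 5.9.2 stops the drug and the discontinuation ground can apply. Symptomatic cases are covered by 7.1.1 and serious ones by 6.5.3. The gap is the asymptomatic, non-serious, reduction-only case.

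**What is still captured.** Date and reason for down titration go into source and eCRF (5.5). Clinical significance and the reason for the abnormality go into source and eCRF (6.5.3). The repeat ECG documents the course (5.9.2). Abnormal or clinically significant ECG findings are tabulated and listed (8.6).

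**Size.** Number affected = QTc triggers × share that are asymptomatic, non-serious and handled by reduction alone × share not judged significant. The documents supply none of the three factors. Scheduled ECGs fall only at baseline, Week 4, Week 24 and early discontinuation or end of treatment (Table 1), which limits how many triggers can be seen.

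**The case against.** The strongest reply is that the gap needs an unlikely judgement: an Investigator would have to regard a QTc change large enough to compel a dose reduction as neither clinically significant nor medically important. The AE definition in 7.1 includes unfavourable signs, 7.3 asks broadly for any unfavourable change in condition to be recorded, and 7.5 expects AE reports to note dose modification. Further guidance may sit in the eCRF completion guidelines, which are not among the documents. This stands to the extent that many such findings would probably be recorded. It does not close the gap, because the ECG-specific rules are narrower than 7.3 and nothing says which prevails.

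A second reply is that the information is captured elsewhere. That is correct. A reader might infer that these events disappear, or survive only as abnormal ECG values; the documents do not support that, given the down-titration record, the significance entry and the repeat ECG. What is missing is AE coding, grading, causality and outcome.

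A third reply is that QTc comes from a single ECG with automatic interval measurement, while 7.7 requires repeat testing before drug is withheld for a related Grade 3 laboratory abnormality. This is a fair caution about what the extra AEs would represent. However, the confirmation in 7.7 governs withholding of drug; the laboratory recording sentence in 7.1.1 carries no such condition.

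A reader might also infer that QT prolongation belongs on the AESI list. The sponsor gives a rationale for its list in 6.5 and 7.1, 5.9.2 ties QT potential to high oral doses, and 1.2.1 reports no clinically important ECG changes in Phase 1. Adding the term is a preference and is not needed to close the recording gap.

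**Conclusion.** The inconsistency is real and narrow. For an asymptomatic, non-serious QTc finding handled by dose reduction alone, AE status depends on Investigator judgement, while a laboratory abnormality leading to the same drug change is a mandatory AE. Such a finding can, not will, be absent from the TEAE and treatment-related tables.

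This rests on reading 6.5.3 and 7.1.1 as the governing rules for ECG findings, and on the unseen eCRF guidelines not already settling the point. A reader might want a count of missing events or a percentage of under-reporting. Any such figure would only restate an assumed QTc rate and an assumed recording rate, neither of which is in the documents, so none is given. The point is a cheap improvement to uniform safety recording; it does not call the safety conclusions into question.

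**What to change.** In 6.5.3 and 7.1.1, extend the existing laboratory sentence to ECG findings: any ECG abnormality that leads to interruption, modification or discontinuation of study drug is recorded as an AE, with CTCAE grade, causality and outcome, whether or not there are symptoms. Carry the same instruction into the eCRF completion guidelines. Leave the QTc thresholds and the dosing actions as they are; this changes recording only.

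The cost is a sentence in each of two sections and an eCRF note. The downside is a few more recorded AEs, some based on one automated ECG reading, so the reported AE frequency may look slightly less favourable.
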